We foresee the duration of the pilot study of approximately 6 months. Recruitment is on a continuous basis; with approximately 4-6 patients recruited at any given time.

Initial recruitment phase is one week, where patients are identified (see recruitment procedures).

Initial recruitment will be 4-6 patients. The patient is recruited for as long as they are an inpatient at the HDU and discontinued at their discharge (or at their request). Subsequent patients are then recruited in the same process to maintain 4-6 patients at any given time in the program for the duration of the pilot study.

PARTICIPANTS

Inclusion Criteria

1. Males 18+ years.
2. Inpatient in psychiatric Male HDU at PMBC
3. Willingness to give informed written consent and willingness to participate to and comply with the study.
4. Literacy in English.

Exclusion Criteria

1. Current substance dependence.
2. Severe cognitive impairment or thought disorder that does not allow participants to consent or follow treatment instructions.
3. Recent time-zone travel (within last 1 month).

STUDY OUTLINE

Interventions

The intervention is an integrated Sleep Program. It comprises of two main components, thrice weekly group sessions and ward environmental initiatives. The overarching aim is to improve sleep through;

1. **Increase daytime activity**, particularly in the morning if possible, with use of the balcony and outdoor areas. It has the ultimate aim of establishing routine. Many patients in a hospital setting experience a lack of activity. For example, patients may spend a lot of time in bed watching TV or napping throughout the day.
2. **Setting regular rhythms** – enhanced light/dark exposure to stabilize circadian rhythms.
3. **Stimulus control and relaxation** – simple breathing techniques, relaxing music through headphones, relaxation on bean bags
4. Encourage patient-driven management through **psychoeducation**, ongoing sleep quality monitoring and feedback, and driving behavioural change in the ward milieu.

The total duration of a patient’s participation in the Program is flexible. However, we consider a 2-week duration as the minimum dose.

Ward environmental initiatives

A number of initiatives are adopted, these are summarised below. They are specific to the participants of the study. Bean bag and visual cues (ward posters) are made available to the participants in their own rooms; while headphones are pre-existing equipment available to all patients in the HDU.

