An adverse event is defined as any untoward medical occurrence in a participant which does not necessarily have a causal relationship with the study treatment. All adverse events will be collected after the participant has provided consent and enrolled into the study. If subject experiences an adverse event after the informed consent document is signed (entry) but the participant has not started to receive study intervention, the event will be reported as not related to stimulus control therapy.

All adverse events occurring after entry into the study and until hospital discharge will be recorded.

If treatment is discontinued as a result of an adverse event, study personnel will document the circumstances and data leading to discontinuation of treatment.

The study will monitor for potential adverse effects at each treatment session or workshop.

Adverse events reported spontaneously or in response to open-ended questions asked routinely at each visit (by the study coordinator, psychiatrist or nurse) will be recorded with a medical evaluation of severity and causality and coded using the Medical Dictionary for Regulatory Activities (MEDDRA), Preferred Terms will be reported.

Serious Adverse Event Reporting

A Serious Adverse Event (SAE) is defined as any untoward medical occurrence that results in the following: death, is life-threatening (that is, imminent risk of death), requires medical inpatient hospitalisation or prolongation of existing hospitalisation, persistent or significant disability/incapacity, condition requiring unnecessary medical or surgical intervention. An SAE can also be a significant hazard as determined by the trial investigators. Serious adverse events occurring after a participant has left the study will not be reported unless the investigators feels that the event may have been caused by sleep consolidation therapy or a protocol procedure. Investigators will determine relatedness of an event based on a temporal relationship to the treatment, as well as whether the event is unexpected or unexplained given the participant's clinical course, previous medical conditions, and any concomitant medications

An SAE also includes adverse event that might have led to death or a serious deterioration in health had suitable action or intervention not taken place:

- 1) A malfunction of device such that it has to be modified or temporarily/permanently taken out of service

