- 2) A factor found on examination of the device (a deterioration in characteristics or performance)

De-identified Serious Adverse Event Reports will be completed as required throughout the study period and sent the ethic committee.

Early Termination

Possible circumstances for early termination of the study include:

1. Early termination initiated by patient due to side-effects, change-of-mind, intolerability, or the perception that their sleep have improved sufficiently such that they no longer require participation in the program.
2. Loss of capacity to consent due to deterioration or variation in mental state
3. Loss of ability to participate due to deterioration or variation in mental state
4. Medical admission of patient due to an acute medical illness whilst inpatient at PMBC
5. Transfer of patient to a different facility.

The study coordinator will be responsible for correspondence with HREC.

Investigators involved in implementing the Sleep Program clinically, can receive formal notification of termination from the participant by verbal or written form. They may receive notice of termination through a delegate (such as the participant's nurse or medical officer responsible). The investigator will need to formally inform the Study Coordinator in written form.

The Study Coordinator will then be required to document termination in digital study data for this participant – whose data will be separated from overall data pool. Early termination data will be kept for discussion purposes but will be excluded in results and statistical analyses.

The Study Coordinator will be responsible for informing the

(who is responsible for what aspect in the process of terminating the study (informing participants, correspondence to HREC, compiling a final study report, unbinding if applicable)).

BLINDING AND UNBLINDING

- a) Blinding (Masking): This trial is an open-label with no attempt at masking
- b) Emergency unblinding: not applicable

STATISTICAL CONSIDERATIONS

Sample Size or Power Calculation

The pilot study will determine the sample size. Power calculation will be the minimum number of samples required to provide adequate power for the primary outcome. (Actigraphic changes in sleep duration)

Statistical Analysis Plan

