Any original study forms will be entered onto the computer as de-identified patient data. The original forms are then kept on file at the [name] Centre. Participant files will be stored in numerical order and in a secure cabinet within an office in the staff-only section (swipe-card access) of the PMBC. All participant files will be maintained for 15 years after the completion of the study.

Dissemination of the outcomes of the project

Sleep Actigraphy data will be identifiable only by Participant ID and will be given directly to the patient and not to any third party. This is part of the feed-back and discussion process in the Sleep Program.

The overall outcomes of the project will be disseminated in a confidential envelope with generalised outcomes (that are not identifiable to any original participant) and sent to the patient or given to the patient (if they are still inpatient in a lower acuity ward).

Findings of this pilot study will likely be submitted for publication in relevant scientific journals.

REFERENCES

- Ancoli-Israel, Sonia, et al. "The Role of Actigraphy in the Study of Sleep and Circadian Rhythms." *Sleep*, vol. 26, no. 3, 2003, pp. 342–392., doi:10.1093/sleep/26.3.342.
- Benca, R. M., Obermeyer, W. H., Thisted, R. A., & Gillin, J. C. (1992). Sleep and psychiatric disorders: a meta-analysis. *Archives of general psychiatry*, 49(8), 651-668.
- Cauter, Eve Van. "Circadian and Sleep-Related Endocrine Rhythms in Schizophrenia." *Archives of General Psychiatry*, vol. 48, no. 4, Jan. 1991, p. 348., doi:10.1001/archpsyc.1991.01810280064009
- Cole, R. et al (1992). Automatic sleep/wake identification from wrist activity. *Sleep*, 15, 461.
- Czeisler, C. A., Weitzman, E. D., Moore-Ede, M. C., Zimmerman, J. C., & Knauer, R. S. (1980). Human sleep: its duration and organization depend on its circadian phase. *Science*, 210 (4475), 1264-1267.

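### Data from men who stop early are excluded from results with no safety exception, and serious events after exit are reported only if investigators suspect a causal link

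*Protocol*

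**What the plan says.** Four parts of the protocol bear on this.

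- **Early Termination.** The listed circumstances include a patient stopping for side-effects or intolerability, loss of capacity or of ability to participate as mental state changes, and "Medical admission of patient due to an acute medical illness whilst inpatient at PMBC". Change of mind, satisfaction with improved sleep, and transfer to another facility are also listed. The man's data are then separated from the main pool, kept for discussion, and "excluded in results and statistical analyses". Nothing is said about safety data.
- **Adverse Event Reporting.** "All adverse events occurring after entry into the study and until hospital discharge will be recorded". If an adverse event leads to discontinuation, the circumstances must be documented. Preferred Terms are to be reported.
- **Serious Adverse Event Reporting.** "Serious adverse events occurring after a participant has left the study will not be reported unless the investigators feels" that there may be a causal link. The exception in full is: "unless the investigators feels that the event may have been caused by sleep consolidation therapy or a protocol procedure". Medical hospitalisation is among the criteria that make an event serious.
- **Duration.** A man is "recruited for as long as they are an inpatient at the HDU and discontinued at their discharge", or leaves earlier at his own request.

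The Hypotheses section predicts that the programme will be well tolerated. The third secondary objective covers tolerability and practicality, and the design section names acceptability and retention among the things the pilot is to examine. Blinding and Unblinding states that the trial is open-label.

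**The concern.** Tolerability is one of the few questions that a small uncontrolled pilot can answer, and men who stop because of side-effects or deterioration carry much of the information on it. A rule that takes early-terminated men out of all results takes out that information too. Study Procedure Risks names worsened sleep and heightened paranoid thinking as possible effects of taking part, and either could plausibly lead to one of the listed reasons for stopping. A favourable tolerability statement could then follow from the exclusion rule and not from the programme.

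The serious-event rule adds a smaller problem. Once a man has left the study, an unblinded judgement of causality decides whether a serious event is reported. The therapy named in that judgement is not the protocol's name for the intervention.

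**Working it through.** The protocol states no sample size (the target is given as not applicable), drop-out rate or adverse-event rate, so there is no figure to reproduce. The check sets the rules side by side.

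**1. Effect of the exclusion on tolerability.** Let N be the men enrolled, E those who terminate early, and h (at most E) those who do so for side-effects, intolerability, deterioration or acute medical admission.

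- Share stopping for harm among all enrolled: h / N.
- Share stopping for harm among the men left after the exclusion: 0 / (N − E) = 0, whatever h is.

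The second result holds for every N, E and h with E < N, because stopping for one of these reasons is itself what places a man in the excluded group. Adverse events that these men had before stopping also leave the reported results if the rule is read literally.

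**2. Overlap with serious events.** Medical hospitalisation makes an event serious, and an acute medical admission is also a listed circumstance for early termination. One event can therefore be a serious adverse event and the reason why its participant is dropped from the results. The overlap is partial: the termination list gives possible circumstances, and prolongation of an existing hospitalisation, which is also serious, is not on it.

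**3. Does leaving the study differ from leaving hospital?** Yes. Participation ends at HDU discharge, on request or by early termination. The dissemination section provides for sending results to a man "if they are still inpatient in a lower acuity ward", so some men may still be in hospital after leaving the study. How many is not stated.

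**4. The safety windows compared.**

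| Event | Rule | Start | End |
|---|---|---|---|
| Any adverse event | recorded | entry | hospital discharge |
| Serious, possibly caused by therapy or procedure | reported | entry | none stated |
| Serious, judged unrelated | reported | entry | leaving the study |

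The third row ends before the first whenever a man leaves the study before he leaves hospital. The gap is that interval, for serious events judged unrelated, and it concerns reporting, not recording.

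**5. Wording of the causality test.** The exception refers to sleep consolidation therapy, a term found nowhere else in the available text. The Interventions section calls the intervention an integrated Sleep Program of group sessions and ward initiatives, and the adverse-event section refers to stimulus control therapy. The added reference to a protocol procedure helps, but does not settle whether goggles, groups and ward measures are all covered.

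**The case against.** The strongest reply is that the safety rules lose much less than they seem to.

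- A reader might infer that serious events have the shorter window in general. The documents do not support that. Events that may have been caused by the study stay reportable with no end date, and the threshold is low.
- A reader might infer that serious events after exit go unrecorded. They are also adverse events by definition, so the recording rule covers them until hospital discharge. Reporting a serious event means a separate report to the ethics committee.
- A reader might infer that a serious event which causes a man to leave is never reported. It occurs before he has left, so the cut-off does not apply, and an adverse event that leads to discontinuation must be documented.
- A reader might infer that the reporting gap falls on the men most harmed. No figure shows this, and a man who leaves because of side-effects is one whose later events could well meet the causality exception.

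It can also be said that the excluded data are kept for discussion, and that the protocol sets no serious-event rate as its test of tolerability.

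The four replies stand, and they confine the serious-event point to events after exit that are judged unrelated. They do not answer the exclusion point. Reporting an event to an ethics committee does not put it in the results, and data held for discussion do not enter a numerator or denominator. The promise to report Preferred Terms does not say that early-terminated men are included, and the Early Termination rule, read literally, says that they are not. Recording after exit is also weaker in practice than on paper: the stated routes are sessions, visits and spontaneous reports, and a man who has left no longer attends sessions.

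**Conclusion.** The concern holds in two parts of unequal weight.

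The main part is the blanket exclusion. As written, it removes from the results the men who stop for side-effects, intolerability, deterioration or acute medical admission, so the tolerability hypothesis would be judged without them. The direction is towards a favourable finding. The size cannot be given, because it depends on how many men stop for these reasons. The conclusion assumes that the exclusion applies to safety data as it does to other data; the text makes no exception.

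The lesser part is the mismatch between the adverse-event and serious-event end points. It affects only serious events between leaving the study and leaving hospital that open-label investigators judge unrelated, and it limits reporting only. It matters mainly because the judgement is unblinded and its reference therapy is misnamed. The documents do not show that serious events are generally less well captured than minor ones.

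The protocol should be changed on both parts. Neither calls for a change to the design or the treatment.

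**What to change.** 1. In Early Termination, state that adverse-event, serious-event and discontinuation data (with reasons) of every enrolled man, including those who stop early, stay in the safety and tolerability summary, with all enrolled men as the denominator.
2. Reconcile the two end points so that serious events recorded up to hospital discharge are also reported, whatever the view on causality. Limit this to what consent and access allow: the Capacity section ends a man's involvement when capacity is lost, and men transferred elsewhere may be out of reach. State how these cases are handled.
3. In the relatedness wording, replace the therapy name with the Sleep Program and say that all its components are meant.

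The cost is redrafting of three short sections, a few more reports to the ethics committee, a decision on consent for events after withdrawal, and possibly a less favourable tolerability figure. No treatment or assessment schedule changes.

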In conclusion, scientific research suggests that in the clinical setting, actigraphy is reliable for evaluating sleep patterns in patients with insomnia, for studying the effect of treatments designed to improve sleep, in the diagnosis of circadian rhythm disorders (including shift work), and in evaluating sleep in individuals who are less likely to tolerate PSG, such as inpatient psychiatric patients. While actigraphy has been used in research studies for many years, it is only recently that the methodological issues have been systematically addressed in clinical research and practice. With those issues addressed, the use of actigraphy is now being applied to clinical practice. (Ancoli-Israel et al, 2003).

STUDY OBJECTIVES

Primary Objective

To evaluate the effect of the Sleep Program on duration of admission in HDU (compared to controls) and sleep duration (Actigraphy data), in male psychiatric HDU inpatient participants.

Secondary objectives

1. Sleep quality - improvement in the Pittsburgh Sleep Quality Index
2. Sleep efficiency- percentage time in bed vs percentage time asleep
3. To test the engagement (tolerability and practicality) with a structured Stimulus Control Therapy Program
4. Impact on use of as needed (PRN) hypnotics
5. To describe the characteristic of sleep, activity and light exposure of patients in a high dependency psychiatric unit using wrist actigraphy.

Hypotheses

- We hypothesise that a structured stimulus control program for sleep will shorten duration of admission at psychiatric HDU.
- There will be an improvement in the sleep duration and efficiency
- There will be an improvement in the quality of sleep via a reduction of the self-rated Pittsburgh Sleep Quality Index score, measured at the beginning and end of the study.
- Participants in the Bright Light Study will engage in a structured stimulus control therapy program and it will be well-tolerated.

STUDY DESIGN

Design, Study Groups, Number of Participants

This is a pilot study for a complex intervention and we do not know the effect of variance. We seek to test our methodology, exterminate recruitment and retention rates, feasibility and finally, determine the sample size. We also seek to highlight any issues with acceptability, compliance, and delivery of our interventions.

Number of centres

Single-centre, at [name] Centre, male High Dependency (psychiatric) Unit

Duration

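### Excluding every early terminator from the results removes the participants who would show poor retention and tolerability, and exposes the effect estimates to selection of unknown direction

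*Protocol*

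**What the plan says.** The Early Termination section lists five circumstances. The first is initiated by the patient: "Early termination initiated by patient due to side-effects, change-of-mind, intolerability, or the perception that their sleep have improved sufficiently". The second and third are "Loss of capacity to consent due to deterioration or variation in mental state" and "Loss of ability to participate due to deterioration or variation in mental state". The fourth is admission for an acute medical illness and the fifth is transfer to another facility. The study coordinator then documents the termination for the participant, "whose data will be separated from overall data pool", and the section ends: "Early termination data will be kept for discussion purposes but will be excluded in results and statistical analyses". It makes no exception by reason, by time on the programme, or for data recorded before stopping.

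The aims are set elsewhere. Secondary objective 3 is "To test the engagement (tolerability and practicality) with a structured Stimulus Control Therapy Program". The section on design, study groups and number of participants says "We seek to test our methodology, exterminate recruitment and retention rates, feasibility and finally, determine the sample size" (the odd verb is evidently a slip for estimating), and adds acceptability, compliance and delivery. The Background gives the first goal as finding the programme's effect, the variance of that effect, and feasibility. The Statistical Analysis Plan section estimates effects by within-person differences of means.

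**The concern.** The rule selects the analysed group on events after enrolment, and several of those events are what the pilot sets out to measure. Someone who leaves because of side-effects or intolerability is evidence on tolerability, and anyone who leaves early is evidence on retention. If both groups are outside the results, the hypothesis that the programme is well tolerated is examined only in those who tolerated it.

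The reasons also include worsening mental state and the feeling that sleep has improved enough. Both plausibly relate to the change in sleep, which the Administrative Information table names as the primary outcome. The primary objective adds length of stay in the HDU compared with controls. Terminators would be removed from the programme side, while no matching exclusion is stated for the comparators. Since the pilot is meant to determine the sample size of a later study, a distorted variance would carry forward.

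**Working it through.** The protocol states no sample size, dropout rate, significance level or test, and says the variance is unknown. There is therefore no figure of its own to reproduce. Every n, stopping share and correlation below is an assumption.

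**1. Retention.** With n enrolled and k early terminators:

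- over all enrolled: (n − k)/n
- after the exclusion: (n − k)/(n − k) = 100%

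For n = 20 and k = 2, 4 or 6, the first gives 18/20 = 90%, 16/20 = 80% and 14/20 = 70%. The second gives 100% each time. This result needs no assumption about why people stop.

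**2. Mean change.** Take the within-person change as normal, in SD units. Let a share a with the worst change and a share b with the best change stop. The retained mean shifts by

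m = [φ(z_a) − φ(z_(1−b))] / (1 − a − b),

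and the retained variance relative to the true one is

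s² = 1 + [z_a φ(z_a) − z_(1−b) φ(z_(1−b))] / (1 − a − b) − m².

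If stopping is only correlated (ρ) with the change, the shift is ρm and the SD ratio is √[1 − ρ²(1 − s²)].

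Example with a = 0.20, b = 0: z = −0.842, φ = 0.280, m = 0.280/0.80 = 0.350. At ρ = 0.5 the shift is 0.5 × 0.350 = 0.175.

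| Worst / best share stopping | ρ | Shift in mean (SD) | Retained SD / true SD |
|---|---|---|---|
| 20% / 0 | 0 | 0 | 1.00 |
| 20% / 0 | 0.3 | +0.105 | 0.98 |
| 20% / 0 | 0.5 | +0.175 | 0.95 |
| 20% / 0 | 1 | +0.350 | 0.76 |
| 0 / 20% | 0.5 | −0.175 | 0.95 |
| 0 / 20% | 1 | −0.350 | 0.76 |
| 10% / 10% | 0.5 | 0 | 0.93 |
| 10% / 10% | 1 | 0 | 0.66 |

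These are large-sample values.

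**3. Later sample size.** For a fixed detectable difference, N is proportional to SD². In the last row, 0.662² = 0.438, so a sample size based on the retained SD would be about 44% of what is needed even though the mean is not shifted. At ρ = 0.5 the ratio is 0.927² = 0.86.

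**4. Adverse events.** The Adverse Event Reporting section records all events from study entry to hospital discharge, reports MedDRA Preferred Terms, and documents the circumstances when an event leads to discontinuation. The Early Termination section excludes terminators' data from results. An acute medical admission is a termination reason, and medical inpatient hospitalisation is part of the SAE definition. For such a participant the two sections give different answers, and neither refers to the other.

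**The case against.** The best defence is that the information is not lost. Enrolment is registered, each termination must be documented, programme usage and adverse events are followed to discharge in the Participant Time Line, and SAE reports go to the ethics committee. A correct retention rate could be built from these records. That stands, and it limits the point in four ways.

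- A reader might infer that terminators' data are thrown away. They are not: they are kept for discussion and left out of analysis.
- A reader might infer that terminators' adverse events disappear. The adverse-event section does not support that. What the documents show is an unresolved conflict between two sections.
- A reader might infer that poor tolerability could never come to light. That is too strong, because the logs would show it. The 100% retention figure follows if the exclusion is applied to the retention count as well, which is the literal reading of the sentence.
- A reader might infer that the sleep effect is certain to be biased, or biased in the programme's favour. Neither follows. Transfer or a change of mind need not track sleep, and one listed reason, "or the perception that their sleep have improved sufficiently such that they no longer require participation in the program", would remove good responders.

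It may also be said that two weeks is the stated minimum dose, so short stayers should not count. The rule is not based on dose, however: someone who terminates in week four is excluded, while someone discharged in the ordinary way before two weeks is not. Keeping data for discussion, without counts over all enrolled, does not deliver a retention or tolerability result.

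**Conclusion.** The sentence is wrong as written and should be replaced. The protocol itself fixes the exclusion, so this is not a detail left to a separate analysis plan.

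The firm part is retention, tolerability and engagement: under the literal rule these results describe only those who stayed, against the pilot's own aims. The possible part is the change in sleep duration, its variance and the length-of-stay comparison. These are open to selection of unknown size and direction. If 20% stop from one tail, the mean shifts by 0.175 SD at correlation 0.5, by 0.350 SD in the extreme case and by nothing at correlation 0, under a normality assumption and shares the protocol does not give. No false-positive rate is offered, because it would need a sample size, a significance level and a test that the protocol does not state.

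**What to change.** Replace the exclusion sentence in the Early Termination section with:

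> All enrolled participants are in the denominator for retention, tolerability and adverse-event results, and terminations are reported by number and reason. Data recorded up to termination are included in the analyses, where consent and ethics approval allow, for every participant with a baseline and at least one later measurement; the number without a later measurement is reported. Length of stay is reported for all enrolled participants where available. An analysis excluding early terminators is shown only as a labelled sensitivity analysis.

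Remove the matching instruction to separate these participants' data from the pool, and state in the Adverse Event Reporting section that its reporting covers all enrolled participants, so that the two sections agree.

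This reduces the selection but does not remove it. A participant who stops before a second measurement has no within-person change. That will matter most for the PSQI, which is completed only in the first and final weeks.

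The cost is a protocol amendment and possibly a less favourable estimate. The data are already collected and kept. Use of data from participants who lost capacity may need ethics review; the consent pages are not available here, so this cannot be settled from the documents.

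### The early-termination exclusion has no exception for adverse events or for the number, timing and reasons of stops; read literally, it removes stops for harm from the results

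*Protocol*

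**What the plan says.** Under Early Termination, the Protocol lists possible circumstances for stopping. The first is "Early termination initiated by patient due to side-effects, change-of-mind, intolerability", to which it adds the patient's view that his sleep has improved enough. The others are loss of capacity to consent, "Loss of ability to participate due to deterioration or variation in mental state", "Medical admission of patient due to an acute medical illness whilst inpatient at PMBC", and transfer to another facility. The study coordinator documents the termination for the participant, "whose data will be separated from overall data pool". The next sentence reads: "Early termination data will be kept for discussion purposes but will be excluded in results and statistical analyses". Neither sentence sets adverse events, the count of leavers or their reasons apart from the rest of a leaver's data.

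Under Adverse Event Reporting, "All adverse events occurring after entry into the study and until hospital discharge will be recorded". Where an adverse event ends treatment, "study personnel will document the circumstances and data leading to discontinuation of treatment". Events are coded in MedDRA and "Preferred Terms will be reported". Nothing there confines the report to men who complete.

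Secondary objective 3 is to test engagement, which the Protocol explains as tolerability and practicality. The last hypothesis is that the program will be well tolerated. The Design section names retention as something the pilot is to establish and says that problems of acceptability are to be brought out. The Statistical Analysis Plan section describes the sample and outcomes and estimates effects by within-person differences of means.

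**The concern.** The exclusion turns on the very thing that a tolerability result should measure. A man who stops because the goggles or the watch distress him, or because his mental state worsens, becomes an early termination, and his data then leave the results. If the rule is followed as written, the reported group is by construction the group in which nobody stopped for harm. A tolerability, acceptability or retention statement from that group would tell the planners of a larger trial little. Mention in the discussion does not repair this, because it supplies neither a rate nor a denominator.

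This is not detail left for a separate analysis plan. The Protocol itself fixes the exclusion, and a later plan would inherit it.

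**Working it through.** The Protocol gives no figure to reproduce: the target sample size is entered as not applicable, and no dropout rate is stated. The check is therefore mainly of the wording, with algebra to show what the literal rule does.

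**1. Reach of the rule.** The exclusion names both results and statistical analyses. The Statistical Analysis Plan section plans description as well as within-person mean differences. On its words, the rule is not confined to the mean differences.

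**2. Who is caught.** Item 1 of the list gives 4 reasons (side-effects, change of mind, intolerability, perceived improvement) and items 2 to 5 give 1 each: 4 + 4 = 8. Five can bear on harm or tolerability: side-effects, intolerability, loss of capacity, loss of ability to participate, and acute medical admission. Three need not: change of mind, perceived improvement, transfer. This counts list entries and not frequencies. The list is not exhaustive, and items 2 and 3 also cover mere variation in mental state, so not every such stop is a harm.

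**3. What the literal rule does.** Let *n* be the number enrolled, *h* the stops for harm, *w* the other early leavers, and *L* = *h* + *w*. All counts below are assumptions for illustration.

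- *Stops for harm.* All enrolled: *h*/*n*. Literal rule: 0/(*n* − *L*) = 0. With *h* = 3 and *w* = 0, *n* = 15 gives 3/15 = 20.0% against 0/12 = 0%, and *n* = 40 gives 3/40 = 7.5% against 0/37 = 0%.
- *Retention.* All enrolled: (*n* − *L*)/*n*. Literal rule: (*n* − *L*)/(*n* − *L*) = 100%. With *n* = 20 and *L* = 2, 4 or 6, true retention is 18/20 = 90%, 16/20 = 80% or 14/20 = 70%. The literal rule gives 18/18, 16/16 or 14/14, which is 100% each time.
- *Overall adverse-event incidence.* Let *a* completers and *b* leavers have an event. All enrolled: (*a* + *b*)/*n*. Literal rule: *a*/(*n* − *L*). The literal figure is lower when *b*/*L* exceeds *a*/(*n* − *L*) and higher when it falls below. With *n* = 20, *L* = 5 and *a* = 2, the literal figure is 2/15 = 13.3%. The all-enrolled figure is 2/20 = 10.0% if *b* = 0, and 5/20 = 25.0% if *b* = 3. The rule can move this measure either way.

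**4. Against the aims.** The first two quantities are what the tolerability objective and the retention aim need, and under the literal rule both are fixed in advance at 0% and 100%.

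**The case against.** The best defence is that the two sections can be read together: Early Termination governs outcome data, while Adverse Event Reporting, with its own collection window and its own reporting promise, governs safety. The surroundings lend this support. Discontinuations for adverse events must be documented, reports of serious events go to the ethics committee throughout the study, and leavers' data are kept for discussion. Enrolment numbers go into a register and each termination is recorded, so a participant flow could be counted.

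Much of this stands. A reader might infer that the two sections certainly contradict each other, or that harms are certain to vanish. The documents do not support that, because the narrower reading is open and serious events have a separate route. But nothing in Early Termination states the narrower reading, and being able to count leavers is not the same as having to report them.

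Two further inferences also go too far:

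- *That the exclusion can only make the program look better tolerated.* This holds for stops for harm. It does not hold for overall adverse-event incidence, because men who leave without an event are removed too.
- *That the rule on serious events after a man has left the study clashes with recording all events to hospital discharge.* Recording and reporting are different acts, and later events thought possibly caused by the therapy or a procedure are still reported. Widening that rule would add work and would depend on consent terms that cannot be seen here.

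**Conclusion.** The point holds as a fault of wording that should be put right. As written, the exclusion has no exception for adverse events or for the number, timing and reasons of stops. Followed literally, it sets stops for harm to zero and retention to 100%, which defeats stated aims of the pilot. Those two results need no assumption beyond the literal reading. Whether the sponsor intended that reading cannot be told from the Protocol. The size of the distortion is unknown, since cumulative enrolment and dropout are not given; the percentages above only illustrate it. Confidence is medium because the narrower reading remains possible.

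**What to change.** Add after the exclusion sentence under Early Termination:

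> This exclusion does not apply to adverse events recorded under Adverse Event Reporting, or to the number, timing and reasons of early terminations, which are reported in the results for all enrolled participants, with all enrolled as the denominator.

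Leave the sentence on serious events after leaving the study unchanged. Do not add wording that endorses leaving early leavers out of the sleep outcome estimates: effect and variance are the pilot's first goal and feed its sample size, so that exclusion is a separate question which this change should not settle by the way.

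The cost is one sentence and one extra table. The events, the circumstances of discontinuation and the terminations are already documented, so no new collection is needed. If the narrower reading was always meant, the sentence simply says so.
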